If a patient has difficulty visiting the study site within three days, the patient can visit a local clinic/hospital to receive rescue therapy for clinical relapse, and then visit the study site during or immediately after rescue therapy for clinical relapse. Alternatively, the examining Investigator may visit the local clinic/hospital to conduct the EDSS/FSS assessment during rescue therapy for clinical relapse.

If the patient is seen at a clinical facility other than the study site, the patient should show the patient ID card which includes the Investigator's contact information to the treating physicians/nurses at the local clinic/hospital and the study site must make every effort to obtain medical records from the facility, including information on treatment administered and the nature of the symptoms and signs observed.

Assessment of relapse is summarized in [Figure 2](#).

Figure 2 Assessment of Relapse

Each extra visit following relapse will be captured in the electronic case report form (eCRF) and a separate Relapse Assessment Form will be completed by the site and sent (e.g., by fax, e-mail) with the accompanying necessary data, into PAREXEL immediately regardless of the assessment of the site staff about whether potential relapse meets protocol-defined relapse and regardless of the time when EDSS/FSS assessment was performed. During the double-blind period, the form and the data will be reviewed by a CEC. The CEC will be able to request additional information to assist in the determination of a relapse if necessary. The CEC will review all cases of relapse and adjudicate each to see if it meets the protocol definition of a relapse. In order to ensure that no relapse events were missed by the Investigator, the adjudication process will include a concurrent review of all cases for potential relapses that may be missed. The relapse which is regarded as a protocol-defined relapse by the CEC followed by confirmation that the EDSS/FSS assessment was performed within seven days after the patient reported the symptoms to the site, will be treated as an event.

The CEC will be comprised of physicians with expertise in NMO and NMOSD. The committee will be responsible for validating each reported relapse event, in a blinded fashion, to determine the event as to whether it meets the criteria of a protocol-defined relapse. Further details regarding the CEC responsibilities and the process of adjudication are described in the CEC charter.

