6.2 DETERMINATION OF SAMPLE SIZE

Approximately 90 patients need to be recruited and randomized in a 2:1 ratio to the two treatment groups (satralizumab and placebo). The sample size considerations are based on the following assumptions:

- A two-sided log-rank test.
- At least 80% power at the 5% significance level.
- The hazard ratio of satralizumab over placebo for an initial 2 months from randomization is 1.0. The hazard ratio after an initial 2 months from randomization is 0.25.
- TFR in the placebo arm following an exponential distribution, with hazard rate for 1 year $h(t) = 1.1295$.
- A 2-year dropout rate of 10%.

Based on the assumptions, 44 TFR events are needed for the primary analysis. The 90 patients enrolled over 33 months and followed for an additional 5 months will provide 44 TFR events. The primary analysis will be performed once 44 TFR events have been observed or 1.5 years after the date of randomization of the last patient enrolled, whichever comes first. The Sponsor will conduct a blind review of the data including accumulation of events during the double-blind period and may take appropriate action such as to increase the number of patients or to extend the double-blind period based on this blind review.

It has been assumed that the number of relapses will follow a Gamma-Poisson distribution and that the variance/mean ratio will be a constant value of $\sqrt{2}$. This distribution was assumed and the ratio was estimated using data from MS trials (Gold et al. 2012; Kappos et al. 2010) because there are no approved medications for NMO and no raw data from patients with this indication are available.

Because the mean ARR of NMO patients is estimated at 0.82 and eligibility criterion 2 says patients at least 1 relapse in last 12 months prior to screening are selected, we calculate the zero-truncated mean of the Gamma-Poisson distribution with the mean of 0.82 and the mean and variance ratio of $\sqrt{2}$, then the baseline ARR is estimated at 1.65. The post-treatment ARR in the placebo group in NMO patients with anti-AQP4 positive and negative is estimated as 1.5 and 1.0, respectively (Cree et al. 2015). Given that the proportion of patients who are negative for anti-AQP4 antibody at screening will be capped at 30% of the total number of patients in this study, post-treatment ARR is estimated as 1.35.

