3 INVESTIGATIONAL PLAN

3.1 Overall Study Design and Plan

This is a multicenter randomized, double-blind, placebo-controlled parallel assignment study followed by an open-label extension (OLE) period. Patients will be randomized to two groups (2:1, Group A or B) and will receive subcutaneous (SC) SA237 (Group A) or placebo (Group B) at Weeks 0, 2, 4, and every 4 weeks (Q4W) thereafter. The randomization will be stratified by prior therapy for prevention of NMO/NMOSD attack (B-cell depleting therapy or immunosuppressants/others) and the most recent attack in the last one year prior to screening (first attack or relapse). If a patient was administered B-cell depleting therapies (e.g. anti-CD20 antibody [e.g. rituximab], anti-CD19 antibody) at least once in the year prior to baseline, the patient will be stratified into "B-cell depleting therapy group" and otherwise into the "immunosuppressants/others group" (e.g. oral corticosteroids, azathioprine, mycophenolate mofetil, cyclosporine, methotrexate, tacrolimus).

Patients who experience a protocol-defined relapse which is adjudicated by the Clinical Endpoint Committee (CEC) in the double-blind period or complete the double-blind period can enter the open-label extension period. The double-blind period of the study ends when the total number of CEC-confirmed protocol-defined relapses is 44. At the end of the double-blind period, the clinical cut-off date for the primary analysis will be on the day of the onset of the protocol defined 44th relapse (adjudicated by the CEC) or 1.5 years after the date of randomization of the last patient enrolled, whichever comes first. In the extension period, patients can receive open-label treatment with 120 mg SA237 SC at Weeks 0, 2, 4, and every 4 weeks (Q4W) thereafter, until commercial availability of SA237 or Sponsor's decision to discontinue the development program.

For patients who experience a relapse in the double-blind period, appropriate rescue therapy for relapse will be administered. For patients who experienced a relapse which is adjudicated by the CEC as a protocol-defined relapse, SA237 should start under stable disease conditions (i.e. Day 31 or later, where Day 1 is defined as the day of onset of a protocol-defined relapse confirmed by CEC). For patients who completed the double-blind

TP-GDO-WW-016-01 Confidential Version 7.0 Effective Date: 28Aug13 Version Date: 28NOV2018

[figure not shown]
Related to: SOP-GDO-WW-019 Page 8 of 60

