4.10.2 Primary Efficacy Variable

The primary efficacy analyses will be based on the ITT population. Supportive evaluations will be performed using the PPS population.

The primary efficacy endpoint is TFR based on protocol-defined relapses confirmed by the CEC with EDSS/FSS assessment performed by the examining assessor within 7 days after relapse symptoms were reported to the site by the subject. TFR is defined as the time from the date of the randomization until the first occurrence of relapse throughout the double-blind period. Time point of relapse onset is defined as time at which the subject

TP-GDO-WW-016-01 Confidential Effective Date: 28Aug13 Version Date: 28NOV2018 Related to: SOP-GDO-WW-019

Version 7.0

experiences any new or worsening neurological NMO/NMOSD symptoms representing clinical relapse(s) which is later confirmed by the CEC as protocol-defined.

Patients will be censored at the end of double blind period for efficacy analysis (see section 4.2).

The primary analysis of the study is to test the equality of the TFR distribution between the SA237 and Placebo arms:

$$H_0$$
: TFR_{SA237} = TFR_{placebo} versus H_1 : TFR_{SA237} \neq TFR_{placebo}

A stratified log-rank test using strata of prior therapy for prevention of NMO/NMOSD attack (B-cell depleting therapy or immunosuppressants/others) and the most recent attack in the last year prior to baseline (first attack or relapse) will be used.

The Kaplan-Meier method will be used to estimate the TFR based on protocol-defined relapse distribution for each treatment group. The Kaplan-Meier curve will provide a visual description of the differences across treatment groups. In addition, estimates of the treatment effect will be expressed as hazard ratio and 95% confidence intervals using a Cox proportional-hazards model (Exact method will be used for tie data). The model will be stratified by prior therapy for prevention of NMO/NMOSD attack (B-cell depleting therapy or immunosuppressants/others) and the most recent attack in the last one year prior to screening (first attack or relapse). Treatment by covariate interactions will be assessed by including the pairwise interaction terms in the Cox proportional-hazards model.

The following summary tables, figures and analyses will be provided for the ITT and PPS:

- A summary table of Kaplan-Meier estimate of TFR (protocol-defined relapse) will be presented by treatment group.

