4.14 Determination of Sample Size

Approximately 90 patients need to be recruited and randomized in a 2:1 ratio to the two treatment groups (SA237 and placebo). The sample size considerations are based on the following assumptions:

• A two-sided log-rank test.

TP-GDO-WW-016-01 Confidential Version 7.0 Effective Date: 28Aug13 Version Date: 28NOV2018 Related to: SOP-GDO-WW-019 Page 37 of 60

- At least 80% power at the 5% significance level
- The hazard ratio of SA237 over placebo for an initial 2 months from randomization is 1.0. The hazard ratio after an initial 2 months from randomization is 0.25.
- TFR in the placebo arm following an exponential distribution, with hazard rate for 1 year h(t) = 1.1295.
- A 2-year dropout rate of 10%.

Based on the assumptions, 44 TFR events are needed for the primary analysis. The 90 patients enrolled over 33 months and followed for an additional 5 months will provide 44 TFR events. The primary analysis will be performed once 44 TFR events have been observed. The Sponsor will conduct a blind review of the data including accumulation of events during the double-blind period and may take appropriate action such as to increase the number of patients or to extend the double-blind period based on this blind review.

It has been assumed that the number of relapses will follow a Gamma-Poisson distribution and that the variance/mean ratio will be a constant value of $\sqrt{2}$. This distribution was assumed and the ratio was estimated using data from MS trials (Gold et al. 2012; Kappos et al. 2010) because there are no approved medications for NMO and no raw data from patients with this indication are available.

Because the mean ARR of NMO patients is estimated at 0.82 and eligibility criterion 2 says patients at least 1 relapse in last 12 months prior to screening are selected, we calculate the zero-truncated mean of the Gamma-Poisson distribution with the mean of 0.82 and the mean and variance ratio of $\sqrt{2}$, then the baseline ARR is estimated at 1.65. The posttreatment ARR in the placebo group in NMO patients with anti-AQP4 positive and negative is estimated as 1.5 and 1.0, respectively (Cree et al. 2015). Given that the proportion of patients who are negative for anti-AQP4 antibody at screening will be capped at 30% of the total number of patients in this study, post-treatment ARR is estimated as 1.35.

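### SAP 3.1 dates the end of the double-blind period by 44 CEC-confirmed relapses without the 7-day EDSS/FSS condition, whereas SAP 4.14 and Protocol 6.2 require 44 TFR events, which carry it

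*SAP*

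**What the plan says.** **Trigger and cut-off, SAP 3.1.** "The double-blind period of the study ends when the total number of CEC-confirmed protocol-defined relapses is 44". The next sentence adds that "the clinical cut-off date for the primary analysis will be on the day of the onset of the protocol defined 44th relapse", as adjudicated by the CEC, or 1.5 years after the last randomization if that is earlier. Neither sentence mentions when the EDSS/FSS was done. This is the only SAP section that dates the cut-off.

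**Trigger, SAP 4.14.** "The primary analysis will be performed once 44 TFR events have been observed". The 1.5-year alternative is not repeated here.

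**Trigger, Protocol 6.2.** "The primary analysis will be performed once 44 TFR events have been observed or 1.5 years after the date of randomization" of the last patient. The same section sets the target: "At least 80% power at the 5% significance level".

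**What a TFR event is.** SAP 4.10.2 bases TFR on protocol-defined relapses "confirmed by the CEC with EDSS/FSS assessment performed by the examining assessor within 7 days after relapse symptoms were reported". Protocol 3.1.4 agrees: a relapse accepted by the CEC, followed by confirmation that the EDSS/FSS was "performed within seven days after the patient reported the symptoms to the site, will be treated as an event".

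**Looser wordings.** The Protocol Synopsis (Length of Study) speaks of relapses, and Protocol 4.3.2.1 of registered relapses. Neither mentions the 7-day limit.

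**The plan foresees confirmed relapses outside the limit.** Under Protocol 3.1.4 every relapse form is sent in and reviewed by the CEC whatever the timing of the EDSS/FSS. Protocol 6.5.3.1 and SAP 4.10.2 plan a sensitivity analysis that drops the 7-day limit.

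**The concern.** The 44th event fixes the cut-off date, and with it the number of events in the primary test. Two sections of one SAP count different things toward that 44. The protocol version does not explain this. SAP v7.0 is read with Protocol 8.2AB and the protocol supplied is Version 10, but SAP 3.1, 4.10.2 and 4.14 all stand in the same SAP.

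If SAP 3.1 is followed as written, a confirmed relapse assessed after 7 days uses up one of the 44 without being a primary event. The patient is unlikely to supply one later: under Protocol 4.3.2.1 a CEC-adjudicated protocol-defined relapse ends that patient's double-blind period, and SAP 4.2 closes the efficacy period the day before the first extension dose. The primary test would then run on fewer than 44 events, and the stated minimum power of 80% could be missed.

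**Working it through.** **Inputs (SAP 4.14, Protocol 6.2).** 90 patients, 60 against 30; accrual over 33 months; placebo hazard 1.1295 per year; hazard ratio 1.0 for 2 months, then 0.25; dropout 10% at 2 years, i.e. −ln(0.9)/2 = 0.0527 per year; two-sided 5% log-rank test.

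**Assumptions.** The test is unstratified, because no stratum sizes are given. Accrual is either uniform or rising linearly, because no pattern is given. Lateness is random and equal between arms. A late relapse is a non-event, censored 29 days after onset (the day before the earliest extension dose on Day 31) or at the cut-off if earlier, following SAP 4.2.

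**Why simulation.** Without the 2-month lag, the Schoenfeld formula gives (1.960 + 0.842)² / [(2/3)(1/3)(ln 0.25)²] = 7.85/0.427 = 18.4, so 19 events, and 99.1% power at 44. The 44 therefore rests on the lag, which this formula does not cover.

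**The plan's own figure.** With 44 primary events, simulated power is 83.8% (uniform) and 82.2% (rising), so the 80% minimum is reproduced. Separately coded runs gave 82.6% to 84.0% (uniform) and 82.1% to 82.4% (rising). Mean time to the 44th event is 33.5 months (uniform) and 37.9 months (rising). The rising pattern matches the plan's 33 + 5 = 38 months.

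**SAP 3.1 applied literally, exactly k of the 44 assessed late** (80,000 trials per setting):

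| k late | primary events (44 − k) | power, uniform | power, rising |
|---|---|---|---|
| 0 | 44 | 83.8% | 82.2% |
| 1 | 43 | 82.8% | 81.3% |
| 2 | 42 | 81.9% | 80.2% |
| 3 | 41 | 80.9% | 79.3% |
| 4 | 40 | 79.7% | 78.3% |

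The loss is about 1 point per late relapse: (83.8 − 79.7)/4 = 1.0 under uniform accrual and (82.2 − 78.3)/4 = 1.0 under rising accrual. Power first falls below 80% at the fourth and the third late relapse respectively.

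**By late share.** The documents give none, so 5% to 20% is an assumed range:

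| late share | mean primary events, SAP 3.1 count | power, SAP 3.1 count (uniform / rising) | power, TFR-event count (uniform / rising) | delay of cut-off, months (uniform / rising) |
|---|---|---|---|---|
| 5% | 41.8 | 81.5% / 80.0% | 84.6% / 84.0% | 1.5 / 1.6 |
| 10% | 39.6 | 79.1% / 77.7% | 85.4% / 85.4% | 3.4 / 3.5 |
| 20% | 35.2 | 74.2% / 73.0% | 87.5% / 87.4% | 8.7 / 8.1 |

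The mean event counts are 44 × (1 − share). Under the SAP 3.1 count, power is about 80% at a late share near 8% (uniform) or 5% (rising). Under the TFR-event count the cut-off falls later.

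**Type I error.** With no treatment effect, rejection is 5.2% to 5.4% under the SAP 3.1 count and 5.1% to 5.4% under the TFR-event count. The choice of trigger makes no material difference.

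Monte Carlo standard error is 0.1 to 0.2 points.

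**The case against.** The strongest reply is that SAP 3.1 is shorthand in a design overview. SAP 4.10.1.4 names the primary endpoint in almost the same words, SAP 3.2.1 also omits the 7-day clause, and where the SAP means the wider set it says so. This stands as a plausible reading. It does not remove the conflict, because SAP 3.1 is the section that dates the cut-off and nothing states that its count is the TFR count.

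A reader might infer that the documents nowhere say whether late-assessed relapses count toward the 44. That goes too far. Protocol 3.1.4 and SAP 4.10.2 define the event, and Protocol 6.2 and SAP 4.14 set the trigger at 44 such events, so under those sections late-assessed relapses do not count. The defect is that SAP 3.1, Protocol 4.3.2.1 and the Synopsis lack the condition and are not reconciled with the rest.

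The harm is also conditional. Protocol 3.1.4 makes assessment within seven days mandatory, so late cases may be few. With two late relapses, power stays above 80% under both accrual patterns.

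Finally, the sponsor's blinded review of accumulating events "may take appropriate action such as to increase the number of patients or to extend the double-blind period based on this blind review". That could make up a shortfall, but the plan does not say which count the review follows.

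**Conclusion.** The point holds as a minor inconsistency between two stated rules for one decision threshold. Applied literally, SAP 3.1 can leave fewer than 44 primary events, at about 1 point of power per late-assessed relapse. The plan has room for two such relapses under rising accrual and three under uniform accrual before power drops below 80%. These figures rest on the plan's design assumptions, an unstratified test, two assumed accrual patterns, and lateness unrelated to treatment arm.

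Three stronger conclusions are not supported. The trial is not shown to be underpowered, since no late share is given and with none late the two counts coincide. The test is not shown to be invalid, since the error rate is about the same under either trigger. And nothing shows that the sponsor used the wider count. The handling of late-assessed relapses in the primary analysis is not in dispute: they are not events, they are censored under SAP 4.2, and they enter the planned sensitivity analysis.

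**What to change.** In SAP 3.1, define both the trigger and the cut-off date by the 44th first relapse that meets the primary TFR definition in SAP 4.10.2, or by 1.5 years after the last randomization, whichever comes first. State that the blinded event review tracks that same count. The endpoint, the censoring rules and the sensitivity analyses stay as they are.

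The change is to wording and needs no new data. Its cost is a later cut-off, by the delays tabulated above. The 1.5-year cap limits the delay; it is reached first in at most 0.4% of simulated trials at 5% late, 0.4% to 2.4% at 10%, and 11% to 25% at 20%.

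Adding the 1.5-year alternative to SAP 4.14, and aligning the Synopsis and Section 4.3.2.1 of Protocol Version 10, are for consistency only. Protocol 1.3 and 3.1.3 show that the double-blind period has ended, so the practical step is in reporting: state which count dated the cut-off, and how many of the relapses counted were assessed after 7 days.

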3.2 Efficacy and Safety Variables

3.2.1 Efficacy Variables

The primary efficacy variable is the time to first protocol-defined relapse (TFR) based on CEC evaluations. TFR is defined as the time from the date of the randomization until the first occurrence of relapse (day of onset as reported by the investigator) throughout the double-blind period.

The secondary efficacy variables include change in Visual Analogue Scale (VAS) for pain score, change in Functional Assessment Of Chronic Illness Therapy (FACIT) Fatigue scale score, change in Short Form generic health survey (SF-36) score, change in EQ-5D score, change in Timed 25-Foot Walk (T25W) score, proportion of relapse-free patients, annualized relapse rate (ARR), change in modified Rankin Scale (mRS) score, change in Zarit Burden Interview (ZBI) score, change in Expanded Disability Status Scale (EDSS)

TP-GDO-WW-016-01 Confidential Version 7.0 Effective Date: 28Aug13 Version Date: 28NOV2018 Related to: SOP-GDO-WW-019

Page 10 of 60

score, change in visual acuity (Snellen chart) score, and change in low-contrast visual acuity (Low-contrast Sloan letter chart [LCSLC]) score.

3.2.2 Safety Variables

The safety variables include incidence and severity of adverse events (AEs), adverse events of special interest (AESIs), SAEs, injection related reactions (IRRs), injection site reactions (ISRs), patient withdrawals due to AEs, vital signs (temperature, systolic blood pressure [SBP] and diastolic blood pressure [DBP] and pulse rate), physical examinations, clinical laboratory tests (hematology, chemistry, and urinalysis), 12-lead ECG, body weight, and suicidality (Columbia-Suicide Severity Rating Scale [C-SSRS]).

4 STATISTICAL METHODS

4.1 Data Quality Assurance

All tables, figures and data listings to be included in the report will be independently checked for consistency, integrity and in accordance with standard PAREXEL procedures.

4.2 General Presentation Considerations

The analyses periods are defined as follows:

- Study duration of double blind period for efficacy analysis
 - Study duration of double-blind period starts on the day of the randomization. The double-blind period ends on the earliest day of 1) clinical cutoff date (CCOD), 2) the day before the first treatment in the extension period, 3) the end of the study, or 4) last contact for patients lost to follow up.
- Double blind period for safety analysis
 - Double blind period starts on the day of first dose of study drug. The double-blind period ends on the same day as the efficacy analysis.
- Study duration of SA237 exposure for safety analysis (for All SA237 analysis)
 - Study duration of SA237 exposure starts on the day of first dose of SA237. Study duration of SA237 exposure ends on the earliest day of 1) CCOD, 2) the end of the study, or 3) last contact for patients lost to follow up.

The definition of summaries by visit is as follows:

- Summaries by visit for double blind period
 - Baseline is defined as the latest data before or on the date prior to first administration with either placebo or SA237. Summarized visits except for baseline are defined as follows. Irregular visits such as unscheduled visit between week X, dose outside the visit window (DOW), extra visit at relapsing, and the end of the study are out of scope. Week X visits are

TP-GDO-WW-016-01 Confidential Version 7.0 Effective Date: 28Aug13 Version Date: 28NOV2018

Related to: SOP-GDO-WW-019

Related to: SOP-GDO-WW-019

directly used for categories of time. In other words, time window is not applied. If there are the same visits data, one representative assessment nearest to the scheduled visit day will be summarized.

- Summaries by visit for All SA237 analysis
 - Baseline is defined as the latest data before or on the date prior to first administration of SA237. Summarized visits except for baseline are defined as follows. Irregular visits such as unscheduled visit between week X, dose outside the visit window (DOW), extra visit at relapsing, and the end of the study are out of scope. Time window is applied as if visit schedules continue in the double-blind period. Middle of each specified day of visit will be used for the range of time window of each visit. One representative assessment nearest to the specified day of visit in time window of each visit will be summarized

Continuous data will be summarized in terms of the mean, standard deviation (SD), median, minimum, maximum and number of observations, unless otherwise stated. The minimum and maximum will be reported to the same number of decimal places as the raw data recorded in the database. The mean, median and SD will be reported to one more decimal place than the raw data recorded in the database. In general, the maximum number of decimal places reported shall be four for any summary statistics.

For categorical parameters, the number and percentages of subjects in each category will be presented at the relevant time point. The denominator for percentage will be based on the number of subjects appropriate for the purpose of analysis. Unless otherwise noted, percentages will be presented to one decimal place. Percentages will not be presented for zero counts and 100% will be presented as an integer. The denominator for all percentages will be the number of subjects in that treatment group within the population of interest, unless otherwise noted. Missing category will only be displayed when there are missing data.

For pharmacokinetic endpoints, concentrations will be analyzed using all reported decimal places, and displayed to the same number of decimal places as recorded in the database. If any samples are collected outside of the protocol defined time window (Appendix 1 in the protocol), the relevant values will be excluded for the calculation of descriptive statistics. Furthermore, if the samples are collected more than 6 weeks after the last study drug administration, the relevant values will be excluded for the calculation of descriptive statistics considering the half-life of IgG. Descriptive statistics will include number of the subjects, geometric mean, geometric coefficient of variation (CV) and the 95% confidence interval for the geometric mean of the concentrations, as well as arithmetic mean, SD, median, minimum, and maximum of SA237 concentrations will be calculated by visit and per defined time window post-dose according to the Pharmacokinetics Per-Protocol Set (PK-PPS). The CV will be presented with 1 decimal place. For the calculation of descriptive statistics, a serum concentration below limit of quantification will be substituted by half of lower limit of quantification (i.e. LLOQ/2). If more than half of the measured values are BLQ at any blood sampling time point, the statistics will not be tabulated for that time point and will be shown as "N.C.".

TP-GDO-WW-016-01 Confidential Version 7.0 Effective Date: 28Aug13 Version Date: 28NOV2018

Page 11 of 60

For immunogenicity, below rules will be applied to neutralizing antibodies:

- Except baseline measurement, neutralizing antibodies will be assessed only if anti-SA237 antibody results are positive.
- If SA237 concentration is over 1 ug/mL, the data of the neutralizing antibodies will be excluded for the calculation of descriptive statistics. High concentrations of SA237 could lead to false negative results in the neutralizing antibody analysis

Changes from baseline in categorical data will be summarized using shift tables where appropriate.

P-values greater than or equal to 0.001, in general, will be presented to three decimal places. P-values less than 0.001 will be presented as "<0.001".

Confidence intervals will be presented to one more decimal place than the raw data.

The Confidence Interval for hazard ratio will be calculated based on the Wald type and the relapse rate Confidence Interval will be provided using Kaplan Meier method with a LOGLOG transformation.

All report outputs will be produced using SAS® version 9.2 or a later version in a secure and validated environment.

